3.7 Sample Collection Procedure

Enrollees who have fulfilled the inclusion criteria would have the details of the study explained thoroughly to them. The parent or guardian will be required to sign an informed consent form once they agree to participate in the study. All enrollees will have a case record form (CRF). The CRF will be used to collect the following details.

1. Socio-demographic, clinical and laboratory details of all enrollees in the study. The CRF will also have the contact information of each enrollee as well as the past medical history.
2. Record details of each visit: These will include clinical details that would be assessed at each clinic visits, including physical examinations, blood film for malaria parasite, and hematocrit values for each enrollee. Any change in contact details or living situation would be noted.

For the enrollees, a medical history will be obtained from parent/guardian including presenting symptoms and current medications. Physical examination will be performed; weight and axillary temperature recorded. A finger prick blood sample will be obtained for thick blood smears and blood spots on filter paper for parasite genotyping. Five milliliters of venous blood sample will also be obtained for assessment of hematological and biochemical parameters.

Blood film for malaria parasite: Thick blood film will be prepared from finger prick sample of each enrollee at each contact time, stained with fresh 10% Giemsa stain at pH 7.2 and read under a light microscope at X1000 magnification. Gametocyte carriage will be specifically looked out for in the thick film on all contact days. Blood spots on filter paper will be obtained at enrollment and at follow up. This will be used for DNA analysis by polymerase chain reaction (PCR) to differentiate re-infection from recrudescence

Blood chemistry and hematology: 5mls of venous blood samples would be taken for clinical chemistry (electrolytes, urea and creatinine as well as a liver function test) evaluation at day 0 and on the follow up days.

Hematocrit measurement: This will be done by the micro-hematocrit method and the result recorded in percentage. The hematocrit will be done at enrolment and at each clinic visit.

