3.7.2 Follow-up

Clinical and parasitological evaluation will be done on each day of follow-up or on any other day if the patient feels unwell. Patients will be reminded by phone calls 30minutes before the next dose of AL and on the day before the follow up visit (all enrollees i.e. PA and AL arms) and those who fail to attend follow up will be visited at home. Transportation fare will be given as incentives to the parents or care givers to encourage attendance for follow up. During each visit, a brief clinical history will be obtained to assess new complaints and possible side effects of medications and a physical examination will also be performed. Hematocrit and chemical analysis (bilirubin, blood glucose, creatinine and liver enzymes- AST, ALT & Alkaline Phosphatase) will be done on at enrolment and follow up on days 3, 7 and 28 to monitor possible changes.

Filter paper blood samples for parasite genotyping will be obtained on day 0, 3, 7, 14, 21 and 28 or earlier if enrollee is symptomatic. A finger prick blood sample will be taken to prepare thick blood smears on days 1, 2, 3, 7, 14, 21, 28 and on any other (unscheduled) visit. The slides will be air-dried away from direct sunlight, stained with fresh 10% Giemsa at pH 7.2 for 15 to 20 minutes and read independently by two microscopists. Parasite density (the number of asexual parasites per μl) will be calculated by counting parasites against about 200 leukocytes and assuming a leukocyte count of 8,000/ μl of blood ³⁶. A smear will be considered negative only after screening at least 200 high power fields. However, a slide will be read against 500 leukocytes before it is declared negative. All discordant smears and slides with a parasite density difference $>10\%$ will be read by an independent microscopist and the PI. For quality control 5% of randomly selected slides will be read by an independent microscopist not involved in the study.

Paired samples (D0 and Day of recurrence) of blood spots on filter paper collected from patients with parasite recurrence on or before D28 will be analyzed using PCR techniques for parasite DNA.

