- **Gametocyte carriage**: proportions of patients with gametocyte at a given point in time using the Area Under the Curve Graph for PA will be compared with that of AL.

3.7.3 Safety parameters will be evaluated as follows:

- Safety will be analyzed in terms of adverse events and severe adverse events using clinical signs, symptoms and laboratory parameters.
- Liver enzymes (ALT/AST) >3 times upper limit of normal (ULN) plus peak total bilirubin >2 times ULN in the absence of a significant alkaline phosphatase increase (= Hy's law) will be deemed as serious adverse effects (SAE).
- ALT and AST >5 times ULN will be deemed an AESI. (see below)

Serious Adverse Events

An adverse event will be considered serious if it fulfils one of the following criteria:

- causes death or
- is life-threatening or necessitates hospitalization or prolongs hospitalization or results in persistent or significant disability/incapacity or is a medically important event constitutes a possible Hy's Law

An example of an important medical event is one that while not-immediately life-threatening might become so if there had been no intervention

In case of SAEs, independent of causality, the healthcare personnel must immediately contact the PI / Investigator for validation of the seriousness and determination of the causality.

Subsequently, the procedure described below must be followed:

- SEND (within 24 hours and pdf scanned documents) the signed and dated copy of the “Adverse Event form” and the form “SAE complementary information” to Shin Poong Pharmacovigilance (PV) (Tel/[contact] or email: [contact])
- Contact immediately (the same day) the medical monitor/Pyramax QPPV responsible for safety in case of death or life-threatening events.
- The follow-up of each fatal or life-threatening AE must be provided to the medical monitor and Shin Poong PV within the same timeline as the initial report (within 24 hours and preferably by email).
- ATTACH to the Case Record Form (CRF) the photocopy of all available results and examinations which were undertaken (and their date). Analysis results must be accompanied by the laboratory normal ranges. Special consideration shall be taken to ensure patient anonymity, and to the correct completion of the patient’s study specific identifier in the copies of the source documents provided to the sponsor.

Causality

All adverse events must have causality assigned by the investigator. As a guide causality can be assigned as follows:

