3.7.4 Adverse event of special interest

An adverse event of special interest (AESI) is an adverse event for which on-going monitoring is appropriate within the context of the study. These events necessitate complementary examinations in order to characterize and understand them.

AESIs in this study can be related to:

Hepatotoxicity

Presenting with fatigue, nausea, abdominal pain itching or signs of jaundice such as dark urine, putty or mastic colored stools, jaundice

And/or

ALT or AST >5 x Upper Limit of Normal (ULN) (Patients with normal baseline LFTS)

Or ALT or AST >3 x ULN and total bilirubin >2 x ULN (Potential Hy's Law)

Or ALT or AST >2 x the baseline value if >2 x ULN at baseline

If these occur then a hepatitis panel should be performed

- Hypersensitivity
 - Flushing, appearance of wheals/urticaria, breathlessness, Faintness and/or fall in blood pressure occurring soon after Pyramax administration

The study team, as well as the relevant referral facilities, should be trained to take particular notice of symptoms/signs suggestive of the AESIs in this study.

In case of an AESI confirmed by the study physician, Shin Poong PV shall be informed within 24 hours by fax or email using the contact details above, even if the event does not satisfy any condition of seriousness. Notification will occur through the use of an AESI form.

Note that AESIs should only be reported as a serious adverse event if they fulfill the criteria for seriousness.

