3.7.5 Follow-up of Adverse Events

The healthcare personnel must take all appropriate measures to protect the safety of the patients. Personnel must ensure to document follow-up of the evolution of each adverse event (clinical, biological or other) until resolution or until the stabilization of the patient's status.

All new relevant information concerning the initial SAE shall be recorded on a form "SAE follow-up information form" by the nursing staff of the health centre, and shall be validated by the PI/co-PI who shall transfer the form to the local person/physician responsible for the pharmacovigilance of the project and Shin Poong PV.

In case of a serious adverse event the patient must be followed until complete resolution and normalization of all analysis results, or until chronicity of the patient's status. This can imply that the follow-up of the patient must continue beyond the period of follow-up per protocol, and that additional investigations could be requested.

DATA ANALYSIS.

Data will be entered into the computer using the Epi-data software. This subsequently would be cleaned and transferred to SPSS Statistic Software version 20 for analysis. The outcome of interest (dependent variable) presented as a categorical variable with, presence of malarial parasitemia, and the level of efficacy reported. The independent or explanatory variable of interest in this study would be use of chemotherapy. All independent variable would be reported as categorical. Proportions of treatment outcome will be compared by using chi square. Normally distributed continuous data will be compared using unpaired student t-test. Mean values will be given as mean \pm SD and values of $P < 0.05$ will be considered statistically significant.

ETHICAL CONSIDERATIONS

This study, will be a prospective randomized open label clinical trial comparing the safety and efficacy of Pyronaridine-artesunate and Artemether-lumefantrine in the treatment of symptomatic acute uncomplicated malaria in Nigerian children aged 3 to 144 months who seek treatment in the study hospital. The studies will be conducted according to Good Clinical Practice and the Declaration of Helsinki.

Confidentiality of data: Personal details of enrollees in the study will be treated with utmost confidentiality, as it is against the principles of good clinical practice to make such information public. Also, codes will be assigned to all participants.

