|---------------|-------|---|-------|---|-------|---|-------|---|-------|---|--------|---|--------|---|--------|---|--------|---|--------|---|-------------|---|-------------|---|--|
| | P | S | P | S | P | S | P | S | P | S | P | S | P | S | P | S | P | S | P | S | P | S | P | S | |
| Date | | | | | | | | | | | | | | | | | | | | | | | | | |
| Chills/Rigors | | | | | | | | | | | | | | | | | | | | | | | | | |
| Fever | | | | | | | | | | | | | | | | | | | | | | | | | |
| Anorexia | | | | | | | | | | | | | | | | | | | | | | | | | |
| Nausea | | | | | | | | | | | | | | | | | | | | | | | | | |
| Vomiting | | | | | | | | | | | | | | | | | | | | | | | | | |
| Diarrhoea | | | | | | | | | | | | | | | | | | | | | | | | | |
| Abd. Pains | | | | | | | | | | | | | | | | | | | | | | | | | |
| Cough | | | | | | | | | | | | | | | | | | | | | | | | | |
| Palpitation | | | | | | | | | | | | | | | | | | | | | | | | | |
| Insomnia | | | | | | | | | | | | | | | | | | | | | | | | | |

Present (P): 0 = Not present, 1= Present, 2 = Not evaluable

Severity (S): 1 = Mild 2 = Moderate 3 = Severe

TREATMENT EMERGENT SIGNS AND SYMPTOMS (TESS)

| Features | Day 0 P S | | Day 1 P S | | Day 2 P S | | Day 3 P S | | Day 7 P S | | Day 14 P S | | Day 21 P S | | Day 28 P S | | EXTRA VISIT | |
|-------------|-----------------|--|-----------------|--|-----------------|--|-----------------|--|-----------------|--|------------------|--|------------------|--|------------------|--|----------------|--|
| Date | | | | | | | | | | | | | | | | | | |
| Pallor | | | | | | | | | | | | | | | | | | |
| Yellow eyes | | | | | | | | | | | | | | | | | | |
| Headaches | | | | | | | | | | | | | | | | | | |
| Rash | | | | | | | | | | | | | | | | | | |
| Reflex | | | | | | | | | | | | | | | | | | |
| Diplopia | | | | | | | | | | | | | | | | | | |
| Fatigue | | | | | | | | | | | | | | | | | | |
| Other | | | | | | | | | | | | | | | | | | |
| Other | | | | | | | | | | | | | | | | | | |

Present (P): 0 = Not present, 1= Present, 2 = Not evaluable

Severity (S): 1 = Mild 2 = Moderate 3 = Severe

.....
LABORATORY RESULTS: LFT & BLOOD CHEMISTRY

| PARAMETER | DAY 0 | DAY 3 | DAY 7 | DAY 27 | DAY 35 | DAY 42 |
|----------------------|-------|-------|-------|--------|--------|--------|
| Date | | | | | | |
| Urea | | | | | | |
| Creatinine | | | | | | |
| Random Blood sugar | | | | | | |
| Total bilirubin | | | | | | |
| Conjugated bilirubin | | | | | | |
| ALT | | | | | | |
| AST | | | | | | |
| ALP | | | | | | |

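### For haematocrit and blood chemistry the plan names only an unpaired t-test and no use of the Day 0 value; analysis of covariance would compare the arms more precisely from the same data

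*Combined protocol and SAP*

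**What the plan says.** Section 3.7.2 (Follow-up) states that haematocrit and chemistry (bilirubin, glucose, creatinine, AST, ALT and alkaline phosphatase) "will be done on at enrolment and follow up on days 3, 7 and 28 to monitor possible changes". Section 3.7 goes further for one of them: "The hematocrit will be done at enrolment and at each clinic visit". The Summary of Activities table agrees with that. The chemistry sheet of the case record form has a Day 0 column beside the follow-up columns: "PARAMETER | DAY 0 | DAY 3 | DAY 7".

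The Data Analysis section, which follows 3.7.5, names two tests. For categorical outcomes: "Proportions of treatment outcome will be compared by using chi square". For continuous ones: "Normally distributed continuous data will be compared using unpaired student t-test". Results are to be given as mean and SD, and P values below 0.05 "will be considered statistically significant"; whether the tests are one- or two-sided is not stated. The section names treatment as the explanatory variable of interest and has all independent variables reported as categorical. It mentions no baseline covariate, change score, repeated-measures model, transformation or rank-based test.

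On safety, section 3.7.3 says: "Safety will be analyzed in terms of adverse events and severe adverse events using clinical signs, symptoms and laboratory parameters". One liver criterion in section 3.7.4 refers to the pre-treatment value: "Or ALT or AST >2 x the baseline value if >2 x ULN at baseline".

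**The concern.** Comparing safety is part of the study aim (section 2) and of the first secondary objective (2.1). The Background lists anaemia and short-lived transaminase rises among the reported effects of pyronaridine-artesunate, and section 3.7.4 makes hepatotoxicity an event of special interest. Haematocrit and the liver tests are thus the laboratory values a reader will most want compared.

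Two things are missing. First, the part of a child's follow-up value that could be predicted from Day 0 is left in the error term unless the analysis uses Day 0, and the plan does not say that it will. Second, the t-test is reserved for normally distributed data. Enzymes and bilirubin are usually right-skewed, so the liver tests may have no planned comparison of values at all. At stake is how small a difference in laboratory values the trial can resolve.

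**Working it through.** **Inputs from the documents.** Allocation is randomised to two arms of equal size. The evaluable target is 70 per arm (section 3.6). The documents give no SD, correlation, power or sample size for any laboratory variable.

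**Check on the 70.** It comes from the cure-rate calculation: variance term 0.964 × 0.036 + 0.989 × 0.011 = 0.045583; denominator (0.05 + 0.025)² = 0.005625. With z-values 1.645 and 1.28, n = 0.045583 × 2.925² / 0.005625 = 69.3, so 70. (The printed z of 1.96 would give 86. That is a separate matter and does not bear on this point.) Here 70 serves only as the number of children with follow-up.

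**Assumptions.** The Day 0 to follow-up correlation r is taken from 0.3 to 0.7, the SD is equal at Day 0 and follow-up, tests and intervals are two-sided at 5%, and the haematocrit SD is 5 points for illustration.

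**Formulas.** The variance of the arm difference, relative to a t-test on follow-up values (= 1), is:

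- t-test on change from Day 0: 2(1 − r)
- ANCOVA on Day 0: 1 − r²
- ANCOVA relative to the change t-test: (1 − r²) / [2(1 − r)] = (1 + r)/2

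The reduction in standard error is 1 minus the square root of the relevant ratio. The per-arm number that a follow-up t-test would need for the same precision is 70/(1 − r²). The difference detectable with 80% power is (1.96 + 0.8416) × √(2/70) = 0.474 SD for the follow-up t-test, and 0.474 × √(1 − r²) for ANCOVA.

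| r | Variance, change t-test | Variance, ANCOVA | SE reduction vs follow-up t-test | SE reduction vs change t-test | Equivalent n per arm | Detectable difference, ANCOVA (SD) |
|---|---|---|---|---|---|---|
| 0.3 | 1.40 | 0.91 | 4.6% | 19.4% | 77 | 0.452 |
| 0.5 | 1.00 | 0.75 | 13.4% | 13.4% | 93 | 0.410 |
| 0.6 | 0.80 | 0.64 | 20.0% | 10.6% | 109 | 0.379 |
| 0.7 | 0.60 | 0.51 | 28.6% | 7.8% | 137 | 0.338 |

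Equivalent n is against the follow-up t-test.

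**Haematocrit example.** The 95% half-width for a follow-up t-test is 1.96 × 5 × √(2/70) = 1.66 points. At r = 0.6 a change t-test gives 1.66 × √0.80 = 1.48, and ANCOVA gives 1.66 × √0.64 = 1.33.

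**Simulation check.** With 70 per arm and 15,000 runs per value of r, the variance ratio of ANCOVA to the follow-up t-test was 0.918, 0.759 and 0.517 at r = 0.3, 0.5 and 0.7, against 0.91, 0.75 and 0.51 in theory. At r = 0 it was 1.009: no gain, and a negligible cost for fitting the covariate.

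**The case against.** **The plan may already use Day 0.** A reader might infer that the t-test ignores the Day 0 value. The documents do not say so. The Data Analysis section does not state which value is tested, and since the samples are taken to monitor change, a t-test on change from Day 0 is a natural reading. This stands: the fault is that the use of Day 0 is unstated. ANCOVA is still the more precise choice on that reading, by the factor (1 + r)/2 in variance, and a change score is less precise than the plain follow-up value when r is below 0.5.

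**Safety does not rest on laboratory means.** A reader might infer that the whole safety comparison is weakened. Section 3.7.3 analyses safety through adverse events, with laboratory values entering largely through thresholds, and one threshold in 3.7.4 already uses baseline. Laboratory means are not a named outcome. This also stands. The gain calculated above applies only where laboratory values themselves are compared.

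**The size is assumed.** Day 0 is acute illness and Day 28 is after treatment, so a low correlation cannot be excluded. At r = 0.3 the gain over a follow-up t-test is only about 5%. Correct, which is why the range is shown.

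**Multiplicity and post-failure values.** Seven parameters at three visits make 21 comparisons, and children who fail treatment receive the alternative ACT before some later samples. Both issues apply equally to the t-tests now planned, so neither is a reason to prefer them.

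**Conclusion.** The point holds for comparisons of laboratory values and no further. The plan names one test for continuous data, restricted to normal distributions, and no use of a Day 0 measurement that it already collects. ANCOVA is at least as precise as either reading of the t-test, apart from the negligible cost of one covariate.

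The size depends on a correlation that the documents do not give: about 5% to 29% off the standard error if follow-up values would have been tested, and about 19% to 8% if change would have been tested, for r from 0.3 to 0.7. The figures against the change t-test also assume equal SDs at Day 0 and follow-up. For variables that are not normally distributed, no percentage applies, because there is no planned method to improve on; that gap exists whatever r is.

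A reader might also infer that chance imbalance at Day 0 makes the planned test invalid. It does not. Allocation is randomised and the t-test's standard error already allows for chance imbalance, so the loss is one of precision. The primary outcome, the sample size and the chi-square comparisons are untouched. This is a free improvement rather than a flaw that threatens the trial's conclusions.

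**What to change.** In the Data Analysis section, replace the t-test for laboratory values with the following:

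- Values at Days 3, 7 and 28 are each compared by ANCOVA, with treatment arm as factor and the Day 0 value of the same variable as covariate. The same model can serve for haematocrit at the other visits where it is measured.
- Right-skewed variables, such as ALT, AST, alkaline phosphatase and bilirubin, are analysed on the log scale at both Day 0 and follow-up.
- Results are reported as adjusted mean differences, or ratios for logged variables, with two-sided 95% confidence intervals.

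The sentence that has all independent variables reported as categorical should make an exception for the Day 0 covariate. The same paragraph should state how values taken after a child has switched to the alternative ACT are handled, and that the laboratory comparisons are supportive if no multiplicity adjustment is made.

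The cost is analysis wording only. No visit, sample or form is added, and the named software (SPSS) can fit the model.

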This study is a randomized open label clinical trial that will compare the safety and efficacy of pyronaridine-artesunate and artemether-lumefantrine in the treatment of malaria among children aged 3 to 144 months who have microscopically confirmed symptomatic *Plasmodium falciparum* malaria. The study will be carried out at the Oni Memorial Children's Hospital, [name]. One hundred and sixty-two children between 3 and 144 months who meet the inclusion criteria will be enrolled after obtaining written or witnessed signed informed consent from the parents or guardian. Details obtained from the enrolee will be entered into a case record form specifically designed for the purpose of accurate documentation. A detailed history and physical examination will be carried out on each enrolee. Finger prick blood samples will be taken from each enrolee for thick blood smear for malaria parasite, haematocrit and blood spots on filter paper. Five millilitres of venous blood will be taken from an arm vein for baseline liver function tests, creatinine and random blood glucose on days 0, 3, 7 and 28.

Enrolees will be randomized into one of two groups. Group one will receive pyronaridine-artesunate while group two will receive artemether-lumefantrine at standard doses. Enrolees will be seen daily from days 0-3, and on days 7, 14, 21 and 28. Study drugs will be administered supervised at standard dosage on days 0, 1, and 2. History taking, physical examination and blood smears will be done at each contact time. Special attention will be paid to adverse effects.

Parasite clearance time, fever clearance time and cure rates will be compared between the two groups. The data collected from the participants will be entered into Epi info version 6 databases and then transferred to SPSS Statistics Software version 20 for statistical analysis.

INTRODUCTION

Background of the study

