2.1 SPECIFIC OBJECTIVES

1. Primary:

To determine the comparative efficacy of pyronaridine-artesunate and artemether-lumefantrine in the treatment of acute uncomplicated malaria in children in south-west Nigeria.

2. Secondary:

- i. To compare the efficacy and safety (crude – ACPR) of pyronaridine-artesunate and artemether-lumefantrine in the treatment of acute uncomplicated malaria in children in south-west Nigeria
- ii. To determine and compare the parasite clearance time and the fever clearance time of pyronaridine-artesunate and artemether-lumefantrine in the treatment of acute uncomplicated malaria in children in south-west Nigeria
- iii. To determine and compare gametocyte carriage between pyronaridine-artesunate and artemether-lumefantrine during treatment of acute uncomplicated malaria in children in south-west Nigeria
- iv. To compare the PCR Corrected cure rates of pyronaridine-artesunate and artemether-lumefantrine in the treatment of acute uncomplicated malaria in children in south-west Nigeria

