Enrollee will be withdrawn from the study if the parent/care giver withdraws consent, enrollee develop serious concomitant illness or report taking other unauthorized anti-malarial medication apart from the study drugs during the follow-up period. Those who withdraw consent will be revolved back to the hospital care while those who develop serious concomitant illness would have immediate medical care given to them and thereafter be referred for specialist care at Oni memorial children's hospital or University College Hospital, Ibadan at no cost to them. Enrollees who fail treatment with either of the two ACTs being evaluated will receive the alternative ACT under supervision.

Daily checks and corrections will be carried out on the CRF of enrollees seen to ensure correctness and accuracy. Blood samples collected from study participants will be transported to the respective laboratories in the University College Hospital Ibadan for analysis of blood chemistry and hematology parameters the same day they are collected. Efficacy parameters will be evaluated as follows:

- **Efficacy evaluation** will be based on WHO criteria of treatment outcome as follows; (1) Early treatment failure (ETF; danger signs or complicated malaria or failure to adequately respond to therapy on days 0–3); (2) Late clinical failure (LCF; danger signs or complicated malaria or fever and parasitemia on days 4–28 without previously meeting criteria for ETF or LPF); (3) Late parasitological failure (LPF; asymptomatic parasitemia on days 7–28 without previously meeting criteria for ETF or LCF); (4) Adequate clinical and parasitological response (ACPR; absence of parasitemia on day 28 without previously meeting criteria for ETF, LCF, or LPF).
- **Recrudescence** will be defined as the recurrence of asexual parasitemia within 28 days following antimalarial treatment comprising the same genotypes that caused the original illness. This is believed to result from incomplete clearance of asexual parasitemia because of inadequate or ineffective treatment.
- **Parasite clearance time**: time from first dose of ACT until first total and continued disappearance of asexual parasite forms.
- **Fever clearance time**: time from first dose until the first time the body temperature (for those with a raised temperature at enrolment) decrease to below 37.5°C and remain so for at least 24 hours.

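### Parasite and fever clearance times are observed only at daily visits to Day 3 and then on Day 7, and the plan names no method that suits such grouped times

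*Combined protocol and SAP*

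**What the plan says.** Secondary objective ii in section 2.1 is "To determine and compare the parasite clearance time and the fever clearance time of pyronaridine-artesunate and artemether-lumefantrine". Section 3.7.2 defines both outcomes as times from the first dose. Parasite clearance is "time from first dose of ACT until first total and continued disappearance of asexual parasite forms". Fever clearance is "time from first dose until the first time the body temperature (for those with a raised temperature at enrolment) decrease to below" 37.5°C, and the temperature must then stay below that level for at least 24 hours.

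The summary sets the visits: "Enrolees will be seen daily from days 0-3, and on days 7, 14, 21 and 28". Section 3.7.2 gives the same days for smears and adds visits on other days only when a child is unwell. In the case record form, the drug schedule has a clock-time column, but the clinical follow-up record has only a date row.

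The Data Analysis section, which follows section 3.7.5, names two tests. For outcomes as proportions: "Proportions of treatment outcome will be compared by using chi square". For continuous data: "Normally distributed continuous data will be compared using unpaired student t-test". The summary measure is mean ± SD, and P < 0.05 "will be considered statistically significant". It names no rank, Kaplan-Meier, log-rank or interval-censored method, no rule for children without a clearance time, and no covariate.

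Section 3.2 separately lists the proportions clear of parasites or afebrile on Days 1, 2 and 3 as secondary outcomes.

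**The concern.** A child first seen clear on Day 2 cleared at some point between 24 and 48 hours. A child first seen clear on Day 7 cleared between 72 and 168 hours. Nearly all recorded values will therefore be 24, 48, 72 or 168 hours. Such data cannot be normal, so the condition attached to the t-test is not met. Read strictly, objective ii has no analysis method. Read loosely, it has an unsuitable one.

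If the t-test is applied anyway, four things follow:

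- Each recorded time is rounded up to the next visit, by as much as 24 hours within the daily visits and 96 hours after Day 3.
- One late value can dominate the SD.
- A child who is withdrawn, or given the alternative treatment for failure, before clearing has no value and drops out. Such children may include the slowest responders.
- A reported mean ± SD in hours suggests a precision that was never measured.

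Fever clearance has two further problems. A first afebrile reading on Day 3 has no scheduled confirming reading until Day 7. The outcome also covers only children with a raised temperature at enrolment, whereas section 3.6.1 also admits children on a history of fever alone.

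**Working it through.** **1. Sample size to use.** The plan states no SD, difference or power for clearance times. Its only size figure is the 70 evaluable children per arm in section 3.6. That figure reproduces with a one-sided 5% level: (1.645 + 1.282)² × [0.964 × 0.036 + 0.989 × 0.011] / (0.05 + 0.025)² = 8.567 × 0.045583 / 0.005625 = 69.4, so 70. The checks below use 70 per arm. For fever this is too many, because only children febrile at enrolment count.

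**2. Effect of one late value.** The split is assumed: 42, 25 and 3 children at 24, 48 and 72 hours.

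- Mean = (42 × 24 + 25 × 48 + 3 × 72) / 70 = 2424 / 70 = 34.6 h. SD (divisor 69) = 13.9 h.
- One of the three moved from 72 to 168 h: mean = 2520 / 70 = 36.0 h. The sum of squares is 42 × 12² + 25 × 12² + 2 × 36² + 132² = 29,664, so SD = √(29,664 / 69) = 20.7 h. That child supplies 132² / 29,664 = 17,424 / 29,664 = 59% of the sum of squares.
- Two moved: SD = 25.7 h.

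**3. t-test on visit times against t-test on true times.** The documents give no clearance-time figures, so the inputs are assumed: log-normal true times, medians 18 to 42 h, coefficient of variation (CV) 0.3 to 0.5, median differences of 4 to 6 h, 2,500 simulated trials per setting. Each time was rounded up to the next scheduled visit.

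- Type I error of the t-test on visit times: about 4.3% to 5.1%.
- Arm means shift up by about 9 to 17 h. SDs rise, for example from 9.3 to 12.6 h, or from 19.9 to 34.4 h.
- True mean differences of 4.1 to 6.8 h appear as 4.5 to 10.4 h, a ratio of about 1.07 to 1.5.
- Power falls by about 5 to 23 points, for example from 69% to 51% and from 87% to 63%.

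**4. Changing the test alone.** On the same visit times, a rank test changes power by about −1 to +10 points against the t-test, and a discrete-time log-rank test by about 0 to +10. An unadjusted complementary log-log model ranges from 5 points worse to 6 better.

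**5. Grouped-time model adjusted for baseline.** Complementary log-log model on the visit intervals, 70 per arm, 600 simulated trials per row, with r the assumed correlation of clearance time with baseline:

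| Medians (h) | CV | r | t-test power | Adjusted model power | Gain (points) |
|---|---|---|---|---|---|
| 24 v 29 | 0.5 | 0.5 | 51% | 68% | 17 |
| 30 v 36 | 0.5 | 0.5 | 44% | 63% | 19 |
| 30 v 36 | 0.5 | 0.3 | 45% | 52% | 7 |
| 36 v 42 | 0.5 | 0.6 | 33% | 57% | 24 |
| 30 v 35 | 0.3 | 0.5 | 66% | 73% | 7 |
| 18 v 23 | 0.5 | 0.5 | 68% | 78% | 10 |

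Each power figure has a standard error of up to √(0.5 × 0.5 / 600) = 2 points. With no true difference, rejection was 4.8% for the t-test and 6.5% for the adjusted model (error about 1 point), so a little of the gain may be a slightly liberal test. A separate simulation with r from 0.3 to 0.5 gave 44% to 69% for the t-test and 58% to 76% for the adjusted model. About 7 to 18 points is a fair summary for that range of r.

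**The case against.** The strongest reply is that the plan never says the t-test will be used for clearance times. The sentence is limited to normally distributed data and fits haematocrit and blood chemistry as well. This stands. A reader might infer that the plan commits to a t-test here, and the documents do not support that. The gap remains, because no other method is named for a stated objective.

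A reader might also infer that the comparison would be invalid or produce false positives. It would not. Both arms share the visit schedule, and type I error holds. The harm is to reported means, SDs, the size of the difference and precision.

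Nor would a better test rescue the comparison. Much of the lost precision comes from the schedule, and step 4 shows how little a change of test alone returns. It is also tempting to say that baseline adjustment removes r² of the variance. That holds for linear regression of the time itself and does not carry over to a complementary log-log model.

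The Day 1 to 3 proportions in section 3.2 suit the data and can be compared by chi-square. They reduce the concern, but they are listed as a separate outcome and do not deliver the clearance-time comparison of objective ii.

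Finally, the 168-hour case is only an illustration. Section 3.7.2 counts inadequate response on Days 0 to 3 as early failure and gives failures the alternative treatment, so some children positive on Day 3 would never reach a 168-hour value. No document says how many would.

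**Conclusion.** The concern holds in limited form. Clearance times are grouped by the visit schedule and cannot be normal, and the plan names only a t-test with mean ± SD for normally distributed continuous data. Objective ii therefore lacks a suitable method, and falling back on the t-test would be a poor choice though not an invalid one.

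The size rests on assumptions, since the documents give no clearance-time distribution and no correlation with baseline density. Under those assumptions a baseline-adjusted grouped-time model gains about 7 to 18 points of power, mostly through the assumed correlation; a weaker true correlation would shrink the gain. The simulations assume a clearance time for every child and 70 per arm, so they do not measure the effect of missing values or of the smaller fever subset.

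These are secondary outcomes. Nothing here touches the primary PCR-adjusted response or the sample size. The plan should be changed, but the trial does not depend on it.

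**What to change.** In the Data Analysis section:

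- Compare arms on both clearance times with a discrete-time (complementary log-log) or interval-censored model on the visit intervals: 0–24, 24–48, 48–72 and 72–168 h, then the later visits. For parasite clearance, adjust for log10 Day 0 parasite density.
- Report the cumulative percentage cleared by each day in each arm, in place of mean ± SD.
- Count a child who fails treatment or is rescued before clearing as not cleared through Day 3, the last daily visit. Do not simply censor at rescue: rescue for failure is informative about clearance, and censoring would bring back the selection described above.
- Censor only losses unrelated to treatment response, at the last assessment.
- For fever, restrict to children with a raised temperature at enrolment, and state how a first afebrile reading on Day 3 is handled when the next scheduled reading is on Day 7.

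The cost is SAP wording, a little more analysis work and a summary less familiar to readers than a mean in hours. The data are already due to be collected, and no extra visits are needed.
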